8.22 Participant intervention acceptability (Aim one): The Patient Experience Questionnaire (PEQ), developed by the investigator, will be used to summarize overall patient-reported acceptability in this study. Summary measures of median/range and mean/SD for total categorical PEQ scores, the time in weeks from the initial to follow-up intervention visit, and the number of completed intervention sessions will be reported.

8.23 Participant pain barriers (Aim two): Attitudinal barriers to pain management will be measured using the BQ-II which measures four attitudinal realms with 27 self-rated questions about pain beliefs. The BQ-II has been used in cancer pain studies with psychometrics demonstrating validity and reliability. For cancer patients, internal consistency of 0.89 (mean 1.52, SD 0.73) was reported and higher barriers were significantly correlated with increased age ($r=0.18$, $P=0.02$).³⁰ The total score for the BQ-II and PSEQ will be calculated at study entry and after the first follow-up visit and scores will be summarized (median/range, mean/SD). The paired difference in PSEQ and BQII will be estimated along with a 90% confidence interval. If additional sessions are completed, the scores for PSEQ and BQII will be plotted over time and trends will be explored with graphical methods. Spearman's correlation between the PSEQ and BQII will be estimated along with a 90% confidence interval at each measured time point.

8.24 Participant self-efficacy (Aim two): The study team will look at the correlation among the measures being explored, described herein: Pain self-efficacy will be measured using the PSEQ. In patients with a history of chronic pain and mean pain level rated at 6.2 out of 10, PSEQ demonstrated excellent internal consistency with an alpha of 0.92 and a test-retest reliability from baseline to three months of $r=0.73$, $P<0.001$.³¹ The total score for the BQ-II and PSEQ will be calculated at study entry and after the first follow-up visit and scores will be summarized (median/range, mean/SD). The paired difference in PSEQ and BQII will be estimated along with a 90% confidence interval. If additional sessions are completed, the scores for PSEQ and BQII will be plotted over time and trends will be explored with graphical methods. Spearman's correlation between the PSEQ and BQII will be estimated along with a 90% confidence interval at each measured time point.

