32.0 Appendix E: Patient Experience Questionnaire

Patient Experience Questionnaire

Study ID # (to be filled out by study coordinator):

Instructions: For questions 1-6, please circle the answer that best describes your experience.

1) Were these sessions talking about pain helpful for you? YES NO NOT SURE

2) Were these sessions worth your time? YES NO NOT SURE

3) Would you recommend this type of pain session to others with pain from cancer? YES NO NOT SURE

4) Were you able to set a goal of something you hoped to achieve by having control of the pain? YES NO NOT SURE

5) Did you discuss your participation in these sessions, or parts of what we talked about, with your healthcare team? YES NO NOT SURE

6) Would you suggest also including caregivers these sessions? YES NO NOT SURE

For question 7, please write as much or as little as you would like to share.

7) Please let the research team know any other thoughts about your experiences with these sessions:

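### The planned acceptability summary is a mean/SD of an unscored PEQ total that, in its middle range, does not separate satisfied from dissatisfied patients

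*Combined protocol and SAP*

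**What the plan says.** Acceptability is part (c) of Aim one and has its own row in the endpoint table of section 8.1, where the PEQ is the only instrument named for it. Section 8.22 states that the PEQ "will be used to summarize overall patient-reported acceptability in this study", and the analysis given is "Summary measures of median/range and mean/SD for total categorical PEQ scores". It gives no confidence interval and no acceptability threshold.

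Appendix E holds the form. The instruction is "For questions 1-6, please circle the answer that best describes your experience"; item 7 is free text. Three items ask for an evaluation:

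- Item 1: "Were these sessions talking about pain helpful for you? YES NO NOT SURE"
- Item 2: "Were these sessions worth your time? YES NO NOT SURE"
- Item 3: "Would you recommend this type of pain session to others with pain from cancer? YES NO NOT SURE"

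The other three closed items have the same response options. Item 4 asks whether the patient could set a goal. Item 5 asks "Did you discuss your participation in these sessions, or parts of what we talked about, with your healthcare team". Item 6 asks "Would you suggest also including caregivers these sessions".

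The form carries no numeric codes, item directions or scoring key. Appendix D, by contrast, says which BQ-II items are reverse scored and that mean scores are analysed. In the session tables of section 9.22 the PEQ appears only at session 4.

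**The concern.** A mean, SD and range need a number for each patient, and the plan does not say how three unordered-looking response options become one. NOT SURE could sit between YES and NO, count with NO, or be left out, and each choice gives a different total.

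Even with a coding agreed, the six items do not all point the same way. A patient who approves of everything but would not bring a caregiver scores lower than one who would, for a reason unrelated to how acceptable the sessions were. Acceptability is a stated purpose of this pilot, so the question is whether its one planned summary can be read as acceptability.

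**Working it through.** **Inputs.** Six closed items with three response options each (Appendix E); a total summarised by mean/SD and median/range (section 8.22); 54 participants (section 6.0); exact 90% intervals as the plan's convention for the feasibility proportion (section 8.21). The plan states no PEQ score range, expected mean or threshold, so it has no PEQ figure to reproduce. The codings below are assumptions, because the plan gives none.

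**Step 1: the total depends on the coding.** Take a patient who answers NOT SURE to all six items.

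| Assumed coding | Total, all NOT SURE | All YES | All NO |
|---|---|---|---|
| YES 2, NOT SURE 1, NO 0 | 6 | 12 | 0 |
| YES 1, otherwise 0 | 0 | 6 | 0 |
| Order on the form: YES 1, NO 2, NOT SURE 3 | 18 | 6 | 12 |

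The same answers land at the middle, the bottom or the top of the numeric range.

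**Step 2: opposite patients can tie.** Patient A answers NO to items 1-3 and YES to items 4-6. Patient B answers YES to items 1-3 and NO to items 4-6. If YES is coded *y* and NO is coded *n* on every item, both totals equal 3*y* + 3*n*. Under 2/1/0 that is 3×2 + 3×0 = 6 for each; with YES as 1 and the rest 0 it is 3 for each. Any coding applied equally to all six items gives this tie. Under 2/1/0 the all-NOT-SURE patient also scores 6.

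**Step 3: how much the total says about items 1-3.** Count YES as 1 and enumerate the 2^6 = 64 YES/not-YES patterns.

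| Total | Possible number of YES on items 1-3 |
|---|---|
| 3 | 0, 1, 2 or 3 |
| 4 | 1, 2 or 3 |
| 5 | 2 or 3 |
| 6 | 3 |

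The ambiguity is in the middle of the range. High totals remain informative.

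**Step 4: sensitivity to item 4.** If item 4 is treated as acceptability, the extremes over items 1-4 no longer tie. YES on 1-4 and NO on 5-6 totals 4, against 2 for the reverse (8 against 4 under 2/1/0). The tie between patients A and B on helpfulness, worth and recommendation remains.

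**Step 5: precision of the alternative.** For an item proportion *x*/*m*, the exact (Clopper-Pearson) 90% interval has as its limits the 5% quantile of Beta(*x*, *m* − *x* + 1) and the 95% quantile of Beta(*x* + 1, *m* − *x*). With *m* = 54 the largest half-width is 0.119, which reproduces the 11.9% that sections 18.3 and 21.2 state for the feasibility proportion. The number of PEQ completers is not given, so a range is shown. Assuming about 90% answer YES, 9/10 gives 61% to 99%, and 49/54 (91%) gives 82% to 96%.

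**The case against.** The strongest case on the other side has five parts.

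- **Items 4 and 5 may belong.** Aim one (c) concerns acceptability of motivational interviewing for setting functional pain goals, so item 4 is close to the construct. The intervention encourages patients to take their goals to their palliative care providers, so item 5 may be read as uptake. This stands. A reader might infer that three of the six items do not measure acceptability, but that is a judgement the documents do not settle. Only item 6 clearly lacks a favourable direction.
- **The tie may be rare.** Exactly 1 of the 20 patterns totalling 3 has no YES on items 1-3. This also stands: the documents give no response frequencies. A reader might conclude that the mean total says nothing about acceptability. That goes too far, since totals of 5 and 6 force at least 2 YES answers on items 1-3.
- **The wording may mean category counts.** The word categorical in section 8.22 allows it, but mean, SD and range of a total score most naturally describe a numeric sum. If counts were meant, the fix simply says so.
- **A missing interval is no special fault.** The total usage rate, also in Aim one, is likewise described without one. This is accepted; the interval is an improvement that comes with using proportions.
- **Nothing turns on the PEQ.** The only feasibility criterion is follow-up completion, and PEQ responses are kept in REDCap (section 9.3), so item-level reporting stays possible. This limits the seriousness of the point but does not make the planned summary interpretable.

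**Conclusion.** The point holds in a limited form. As written, section 8.22 summarises acceptability by a total that has no scoring rule, gives NOT SURE no value, and includes at least one item with no favourable direction. Counting YES as 1, a total of 3 is compatible with every result from 0 to 3 on the three evaluative items, while 5 or 6 implies at least 2. Adding median and range does not help, because they describe the same undefined total.

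This rests on reading the plan's phrase as a numeric sum with one coding for all six items. An item-specific coding could break the ties, but none is documented. How often ties would occur is unknown. The matter is worth correcting because acceptability is an Aim one endpoint; it does not affect the feasibility criterion or the conduct of the study.

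**What to change.** In section 8.22, replace the total-score summary with the following.

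1. For each of items 1-6, report n (%) answering YES, NO and NOT SURE.
2. Report acceptability as the proportion answering YES to item 1, to item 2, to item 3, and to all three, each with an exact 90% confidence interval. Count NOT SURE as not YES, which is the conservative choice, and say so in advance.
3. State the denominator: PEQ completers, shown out of all enrolled. Section 7.1 allows participation to end after two sessions and the form is scheduled only at session 4, so the proportions describe those who reached it and should be labelled that way.
4. Describe items 4-6 separately and do not sum them with items 1-3.

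The cost is wording only: the same form, the same data and no added burden for patients. The single summary number is lost, and with few completers the intervals will be wide, which is information a reader of a pilot needs.

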3.0 Objectives*

Purpose: To evaluate the acceptability and feasibility of using a cognitive behavioral intervention called motivational interviewing (MI) to help persons with pain from cancer set goals for managing their pain and improving pain control. Using MI, in our study the researcher will guide patients in goals-focused discussion of their cancer pain. At this time, there are no tested methods that clinicians can use for helping patients set these kinds of functional cancer pain goals (FPGs), despite the importance goal-setting in planning and managing healthcare behavior interventions. The study aims are:

Aim one: Evaluate the feasibility of motivational interviewing with regard to a) completion rate of a baseline and at least one follow-up study visit; b) the number of completed sessions; and c) patient acceptability of nurse-led motivational interviewing to set FPGs in the ambulatory palliative care setting.

Aim two: Explore relationships between patient-reported pain self-efficacy, attitudinal barriers to pain, and observed engagement in a motivational interviewing intervention focused on FPGs.

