8.0 Study Endpoints*

8.1 Data collection instruments:

To measure the study endpoints outlined in the specific aims, we will use the following instruments:

Intervention Feasibility (Aim 1)	Rate of participants completing at least two MI intervention sessions; study spreadsheet
Participant Total Intervention Usage (Aim1)	Rate of completed interventions out of four possible; study spreadsheet
Patient Intervention Acceptability (Aim 1)	Patient Experience Questionnaire (investigator-developed)
Attitudinal Barriers (Aim 2)	Barriers Questionnaire II (Ward & Gunnarsdottir, 2002)
Pain Self-Efficacy (Aim 2)	Pain Self-Efficacy Questionnaire (Nicholas, 1989)
MI Patient Engagement in Goals-Setting (Aim 2)	Observed Engagement Table (investigator-developed)
MI Fidelity	Motivational Interviewing Skills in Health Care Encounters (Petrova et al., 2015)

8.2 Measures:

8.21 Intervention feasibility (Aim one): Feasibility and total intervention usage rates will be calculated by extracting number of visits per participant from the research study registration spreadsheet. Intervention feasibility will be assessed by calculating the proportion of enrolled participants completing at least one follow-up MI session (at least two sessions total). The proportion of patients completing at least one follow-up intervention session will be estimated along with an exact 90% confidence interval. The MI intervention will be considered feasible if a 60% follow-up completion rate can be reached. With 54 participants, at least 26 (41%, 90% CI 36-60%) need to complete a follow-up interview to ensure that the upper bound of the exact 90% confidence interval contains 60%. Feasibility will be met for all participants completing at least two MI intervention sessions. The total intervention usage rate for each participant will be described by the number of interventions sessions attended divided by the total possible number of interventions sessions reported as the sample mean; the usage rate will be described (mean/std, median/range)..

Testing Feasibility of Motivational Interviewing for Patient-Reported Cancer Pain Goals

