8.25 Participant engagement in goal-setting (Aim two): Observed Engagement will be evaluated using the instrument developed by the investigator for this study in which behaviors indicative of active goal setting will be tabulated by the PI or RA. Observed engagement will be summarized categorically, and salient quotes will be extracted into the OET to give voice to participant experiences in study results dissemination.

8.25.1 The study team will look at the correlation among the measures being explored, specifically, pain barriers (BQII) and self-efficacy (PSEQ). The paired difference in BQII and PSEQ scores from sessions one and four will be estimated, along with a 90% confidence interval. If additional sessions are completed, the scores for BQII and PSEQ will be plotted over time and trends will be explored with graphical methods. Spearman's correlation between BQII and PSEQ will be estimated along with a 90% confidence interval at each measured time point.

8.26 MI intervention fidelity: Fidelity to MI methods will be assessed on 33% of interviews using the MISHCE which was developed specifically to measure fidelity in brief healthcare encounters. MISHCE evaluates the degree to which the person providing the MI session follows five domains key to MI. The domains are: 1) MI philosophy, 2) health interviewing, 3) motivation, 4) MI principles, and 5) interpersonal process. Each domain has specific behaviors that are rated as 1) deficient, 2) developing, 3) accomplished, or 4) N/A. MISHCE demonstrated acceptable internal consistency (0.75, CI 95%), good inter-rater reliability (15 of 22 intraclass correlation coefficients were excellent, 5 were good, 1 was fair and 1 was poor), and good-to-excellent test-retest reliability.³² Fidelity assessment will be conducted by the PI or RA.

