9.0 Procedures Involved*

Testing Feasibility of Motivational Interviewing for Patient-Reported Cancer Pain Goals

9.1 Study design:

This is a single-arm pilot study to assess feasibility and acceptability of a motivational interviewing intervention which will entail two-to-four intervention sessions per participant, participant completion of a battery of questionnaires specific to the intervention session, an investigator-led MI intervention at each session, and summary statistics (described below).

9.2 Study Procedures:

After written informed consent has been obtained and verbal consent confirmed participation in this study will involve between two and four intervention sessions.

9.21 Study Participation Compensation: Participants will be compensated with \$25 gift cards at the first and last visits (anticipated to be visits 1 and 4). Pending receipt of additional funding for participant compensation, participants may also be compensated at visits 2 and 3, if these are in addition to the first and last visits, and if this funding is granted to the research study.

9.22 Intervention Sessions: Each intervention session will include a battery of questionnaires, an MI intervention, and the investigator completing a goal(s) summary for the participant to take away. Participants may opt to complete Intervention Sessions 2, 3, and 4 in person on the DFCI campus or via telephone (or a mix). Session-specific content is outlined below. Session-specific content outlined below.

Testing Feasibility of Motivational Interviewing for Patient-Reported Cancer Pain Goals

Session 1:

Questionnaires:	Demographics survey* Pain location diagram (paper and pencil) BQ-II* PSEQ*
MI Intervention	Investigator-led discussion (described below)
Goals Summary	Completed by investigator
Gift Card (\$25)	Disbursed

* Paper and pencil form or tablet computer per participant preference.

Sessions 2 & 3:

Questionnaires:	BQ-II* PSEQ*
MI Intervention	Investigator-led discussion (described below)
Goals Summary	Completed by investigator
Gift Card (\$25)	None (Pending additional funding)

* Paper and pencil form or tablet computer per participant preference.

Session 4:

Questionnaires:	BQ-II* PSEQ* PEQ*
MI Intervention	Investigator-led discussion (described below)
Goals Summary	Completed by investigator
Gift Card (\$25)	Disbursed

* Paper and pencil form or tablet computer per participant preference.

Testing Feasibility of Motivational Interviewing for Patient-Reported Cancer Pain Goals

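### Aim 2 asks how observed engagement relates to self-efficacy and barriers, but the plan only describes engagement and estimates neither relationship

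*Combined protocol and SAP*

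**What the plan says.** Section 3.0 states Aim two as: "Explore relationships between patient-reported pain self-efficacy, attitudinal barriers to pain, and observed engagement in a motivational interviewing intervention focused on FPGs". The instrument table in section 8.1 makes engagement an endpoint of that aim, with the OET as its instrument: "MI Patient Engagement in Goals-Setting (Aim 2".

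For engagement itself, section 8.25 says that "behaviors indicative of active goal setting will be tabulated by the PI or RA", and then: "Observed engagement will be summarized categorically, and salient quotes will be extracted into the OET".

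The only analysis that links one Aim 2 measure to another is a Spearman correlation. Sections 8.23 and 8.24 both say that the "correlation between the PSEQ and BQII will be estimated along with a 90% confidence interval at each measured time point". Section 8.24 has a broader lead-in: "The study team will look at the correlation among the measures being explored, described herein: Pain self-efficacy will be measured using the PSEQ". Section 8.25.1, directly beneath the engagement paragraph, repeats that lead-in and restricts it: "The study team will look at the correlation among the measures being explored, specifically, pain barriers (BQII) and self-efficacy (PSEQ". Section 11.1 refers back to section 8.2 for the analysis and adds none of its own.

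**The concern.** The aim puts engagement beside the two questionnaires as something to be related to them. The analysis leaves it out of every between-measure estimate. A team that follows section 8.2 exactly will report how self-efficacy and barriers go together, and separately what engagement looked like. It will not report whether participants who engaged more had higher self-efficacy or fewer barriers, so that part of Aim 2 goes unanswered.

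The second risk is a late repair. No participant-level engagement variable is named. If the association is added once the data are in, the analyst can choose among a total count, counts per category, presence or absence, or the number of categories seen, with the results already visible.

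**Working it through.** **The plan's own figure.** The documents give no precision for the Aim 2 correlations. Their only such figure, in sections 18.3 and 21.2, is that the exact 90% interval for the follow-up completion proportion is no wider than ±11.9% with 54 participants. It reproduces: the largest Clopper-Pearson half-width is 0.1189, at 27/54 (0.381 to 0.619). It concerns Aim 1 and has no bearing on this point.

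**Coverage of Aim 2.** Three measures form 3 × 2 / 2 = 3 pairs.

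| Pair | Planned estimate | Where |
|---|---|---|
| PSEQ with BQ-II | Spearman, 90% CI, each time point | 8.23, 8.24, 8.25.1 |
| OET with PSEQ | none | – |
| OET with BQ-II | none | – |

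One pair has an estimate, stated three times. No correlation, model, cross-tabulation or plot links the OET to either scale.

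**Could the missing estimates be made from planned data?** Section 9.22 says "Each intervention session will include a battery of questionnaires, an MI intervention, and the investigator completing a goal(s) summary", and its session tables list BQ-II and PSEQ at all four sessions. The OET in Appendix F has a count column for each of six rows, so it yields numbers. The session tables do not list the OET, and section 8.25 does not say at which sessions it is completed. The study schema, which may say, is not shown. Pairing an OET with the same session's questionnaires is therefore possible only where an OET exists.

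**Number of added estimates.** One engagement variable against two scales gives 2 per session with an OET, so at most 2 × 4 = 8. Analysing the six rows separately would give 6 × 2 = 12 per session. With no true relationship, 12 × 0.10 = 1.2 of those 90% intervals would be expected to exclude zero by chance. That favours a single variable.

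**Precision of an added correlation.** Near zero, the 90% half-width for a Spearman correlation is about tanh(1.645 × √(1.06/(n − 3))).

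- n = 54 (full sample): tanh(1.645 × √(1.06/51)) = tanh(0.237) = 0.233.
- n = 26 (the follow-up count in section 8.21): tanh(1.645 × √(1.06/23)) = tanh(0.353) = 0.339.

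With variance 1/(n − 3) instead, these become 0.226 and 0.330. At an assumed correlation of 0.3, the intervals are about 0.07 to 0.50 (n = 54) and −0.04 to 0.58 (n = 26). The formula ignores ties, which a short count score will have, so these figures are approximate. The planned PSEQ with BQ-II correlation has about the same width at the same n.

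**The case against.** The best defence is that exploring relationships does not promise three coefficients. Section 9.1 describes a single-arm pilot with summary statistics, and section 8.25 treats the OET as partly qualitative. A descriptive account of engagement might be all that was meant. This stands to the extent that the count of one pair in three depends on reading the aim pairwise. It does not supply a link between engagement and the scales: describing engagement alone relates it to nothing. If description was the intention, the aim claims more than the plan delivers.

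A second defence is the general lead-in of section 8.24, which could be read as including engagement. What follows it names only PSEQ and BQ-II, and section 8.25.1 restricts the same phrase to those two. Even on the generous reading the analysis could not be run, because no engagement variable is defined.

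A third is that correlations with an unvalidated measure in a small pilot would be imprecise. That is true and belongs in the limitations, but the plan already accepts the same imprecision for the pair it keeps.

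A reader might go further and infer that engagement is not analysed at all, that Aim 2 fails as a whole, or that OET timing was left undefined. The documents do not support these readings. Engagement has a descriptive analysis, the PSEQ with BQ-II correlation is planned, and the schema that may give the timing is not shown.

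**Conclusion.** The mismatch is real. As written, the plan estimates one of the three relationships that Aim 2 can be read to cover, and neither of the two that involve engagement. The size is limited: Aim 2 is exploratory, no error rate or decision rule changes, and the Aim 1 feasibility conclusion is unaffected. It is worth correcting because the correction is cheap and the aim is the study's own.

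The conclusion rests on the text of sections 3.0, 8.1, 8.2 and 11.1 and needs no numerical assumption. The precision figures, which bear only on the cost of the fix, assume n and a correlation near zero. A reader might take 26 as the smallest sample, but it is not a floor. It is the number in section 8.21 who need at least one follow-up session, and section 7.1 allows a second session to be the last, so sessions 3 and 4 may have fewer participants and wider intervals.

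**What to change.** In section 8.25.1, replace the restriction to BQ-II and PSEQ with all three pairs, and name one participant-level engagement variable before analysis. One workable choice is the number of the six OET rows observed at least once in the session. Analyse it within session only, and leave out the Patient suggestions used row at session 1, because its example in Appendix F refers back to an earlier session. The score then runs 0 to 5 at session 1 and 0 to 6 later. A rank correlation within a session does not need a common maximum across sessions.

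Estimate the Spearman correlation of this variable with PSEQ and with BQ-II, each with a 90% CI, at those sessions where an OET is completed. Label the results exploratory and report the number of usable OETs, since section 17.0 makes recording subject to permission each time.

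The cost is a sentence or two in 8.25.1 and at most two extra estimates per session with an OET. No new type of data is needed. If the OET is meant for only some sessions, the estimates should be confined to those; extending it to more would add coding work. The estimates will be imprecise, and the measure is unvalidated and may partly reflect talkativeness or session length, which should be stated as a limitation.

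If engagement is meant to be descriptive only, the alternative is one sentence in section 3.0 that narrows Aim 2 to the relationship between self-efficacy and barriers, with engagement described alongside.

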7.0 Study Timelines*

7.1 Participant duration in study:

Each participant will be enrolled in the study for the time it takes to return for their four scheduled intervention sessions, as long as those visits end by the time data collection closes, at the end of study month 10 (August 2019). The exact duration for each participant will be dependent on their clinic schedules with which the MI study intervention sessions will be aligned, as well as how many of the four MI intervention sessions individual participants complete. An example of brief participation is a participant who completes the initial session and returns for a second and final session one week later. An example of full participation is a participant who completes the initial session and returns for a total of four sessions prior to the study ending. Please see the study schema for a graphic depiction of the study timeline.

7.2 Estimated study completion time:

We anticipate that this research study will be ongoing for one year. Recruitment will occur over nine months. Data collection will begin at the time of recruitment and end when the last participant recruited in that period has completed up to four intervention sessions. Data analysis will take approximately two months. Complete analysis and processing of results is anticipated to conclude twelve months after the first day of recruitment.

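### Does the session one-to-four change in 8.25.1 conflict with the first-follow-up change in 8.23 and 8.24?

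*Combined protocol and SAP*

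**What the plan says.** Sections 8.23 and 8.24 carry the same analysis text. "The total score for the BQ-II and PSEQ will be calculated at study entry and after the first follow-up visit", and the scores are then summarised. Next: "The paired difference in PSEQ and BQII will be estimated along with a 90% confidence interval". That sentence names no sessions, but after the one before it the natural meaning is study entry to first follow-up. Scores from any further sessions are plotted, and a Spearman correlation between the two scales is estimated with a 90% interval at each time point.

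Section 8.25.1, under the heading on engagement in goal-setting, repeats this for the same two scales with a different end point: "The paired difference in BQII and PSEQ scores from sessions one and four will be estimated, along with a 90% confidence interval". It goes on: "If additional sessions are completed, the scores for BQII and PSEQ will be plotted over time". The Spearman sentence follows again.

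The maximum is four sessions; the table in 8.1 describes usage as "Rate of completed interventions out of four possible". Not everyone is expected to reach the fourth. Section 7.1 explains: "An example of brief participation is a participant who completes the initial session and returns for a second and final session one week later". The session tables in 9.22 list both questionnaires at every session. Section 11.1 gives no analysis text of its own for these scores and refers back to section 8.2.

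**The concern.** The same change analysis appears with two end points and no stated relation between them. If the session-four contrast were meant to replace the first-follow-up contrast, everyone who stops after two or three sessions would drop out of the change analysis, although two sessions count as completion in 8.21. If both were reported without denominators, a reader could take estimates from two different groups for one trajectory.

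The further-sessions sentence adds to the doubt. After a contrast ending at the first follow-up it does useful work. After a contrast ending at session four nothing later can exist, so it reads like text carried over from 8.23 and 8.24 when the end point was edited.

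The calendar could also separate the two groups. Section 7.2 says "Recruitment will occur over nine months", and 7.1 closes data collection at the end of study month 10. A late recruit might have time for session two but not for session four.

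**Working it through.** The plan gives no precision or sample-size figure for the paired differences, so there is no figure of its own to reproduce. Its 11.9% half-width (18.3 and 21.2) concerns the feasibility proportion.

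**1. Do the two contrasts exclude each other?**

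- 8.23 and 8.24: study entry to first follow-up, by implication.
- 8.25.1: session one to session four, stated.
- 11.1: refers to section 8.2 without ranking or excluding any part.
- 9.22: both scales collected at sessions 1, 2, 3 and 4.

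Nothing says that one replaces the other. An analyst who carries out every listed analysis produces an early change and a full-course change, and the data for both exist.

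**2. Does the further-sessions sentence contradict 8.25.1?** Only if additional must mean after session four. Section 9.21 uses the idea differently: it treats visits 2 and 3 as extra to the first and last visits, which it expects to be visits 1 and 4. Read that way, 8.25.1 estimates the one-to-four difference and also plots the sessions in between. Someone with a session-four score will normally have had sessions 2 and 3, so the condition is redundant. It does not conflict with the contrast.

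**3. How far could the two groups differ?** Inputs: 54 participants (6.0) and a 60% target for at least one follow-up (8.21). Retention after session two is not given, so a range q per session is assumed.

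- With a session-two score: 54 × 0.60 = 32.4, about 32.
- With a session-four score: 32.4 × q².
- Half-width of the 90% paired-t interval, in SDs of the difference: t(0.95, n−1)/√n.

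| q | n at session four | half-width (SD) |
|---|---|---|
| 0.6 | 12 | 0.52 |
| 0.7 | 16 | 0.44 |
| 0.8 | 21 | 0.38 |
| 0.9 | 26 | 0.34 |
| 1.0 | 32 | 0.30 |

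The first-follow-up contrast, with n = 32, has a half-width of 0.30 SD. The later estimate can be clearly less precise, and each interval will show its own precision.

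**4. Does the calendar matter?** Assume even accrual, and extend to the later sessions the 1-to-4-week return interval that 18.3 gives for a return visit. With 4.35 weeks per month, recruitment lasts 9 × 4.35 ≈ 39.1 weeks, and 4.35 weeks remain after the last recruit. Share cut off = max(0, weeks needed − 4.35)/39.1.

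- Session four needs 3 intervals. At spacing of 1, 2, 3 or 4 weeks that is 3, 6, 9 or 12 weeks, giving 0%, 4.2%, 11.9% or 19.6%, or about 0, 2, 6 or 11 of 54.
- Session two needs 1 to 4 weeks, always under 4.35, so nobody is cut off.
- If session one waits one interval after consent (allowed by 24.2), session four needs 4, 8, 12 or 16 weeks, giving about 0, 5, 11 or 16 of 54. Session two then needs 2, 4, 6 or 8 weeks, giving about 0, 0, 2 or 5.

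All these counts become zero if accrual finishes in three months, as 18.3 and 21.2 estimate: 7 × 4.35 ≈ 30.4 weeks remain against at most 16 needed. They also vanish if 7.2 is read as keeping collection open for the last recruit. The telephone option for sessions 2 to 4 might shorten the spacing. Rewording 8.25.1 would not alter who has time for session four.

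**The case for a change.** The best case for a change is that it costs almost nothing. Naming the sessions in 8.23 and 8.24 and stating that 8.25.1 is additional would settle in advance a choice that could otherwise be made after the results are seen. The text does leave the relation unstated, the repeated block does look like a copy with one phrase altered, and the two contrasts can rest on different people.

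Those observations stand. The harm does not follow from them. It needs the replacement reading, which no sentence supports. Even on that reading, participants who stop at two or three sessions would lose only the paired difference: they would remain in the score summaries at entry and first follow-up and in the Spearman estimates, and those with a third session would also be in the plots. Selective choice after the fact has little room when the plan lists both contrasts and asks for an interval around each.

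It could also be asked whether the first-follow-up score precedes or follows the session-two interview. The tables in 9.22 list the components of a session without fixing their order, and the wording may refer only to when the total is calculated. This does not establish an error either.

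**Conclusion.** The concern does not call for a change. The relation between the two contrasts is unstated, but the plan as written yields both: an early change and a full-course change for each scale. At most, the further-sessions sentence in 8.25.1 is redundant.

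The effect on any decision is nil. Aim two is exploratory estimation in a single-arm pilot, and the feasibility criterion in 8.21 uses session counts only. The possible difference in who is analysed (about 32 against 12 to 32 participants in the illustration) depends on assumed retention. The calendar effect (0 to 16 of 54 for session four) depends on assumed accrual and spacing, and drops to zero under the plan's own three-month accrual estimate. Neither would be altered by rewording. Giving the number of participants with each estimate, as an analyst would ordinarily do, is enough to stop the two being read as one trajectory.

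This conclusion rests on reading section 8.2 as a list of analyses all to be carried out, which is how 11.1 refers to it.
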